2.3 Study Treatments and treatment assignments

2.3.1 Treatment Groups

The three treatment groups to be assessed in this trial are described below

Table 2-1: Treatment Groups

Group	Description
1	DA-9805 (45 mg/day – 15mg TID) for 12 weeks
2	DA-9805 (90 mg/day – 30mg TID) for 12 weeks
3	Placebo (0 mg/day) for 12 weeks

2.3.2 Method of Treatment Assignment, Randomization Ratio, and Stratification

The randomization in this multi-center study will be applied centrally across the sites and will use a mixed block size of 3 and 6 with a 1:1:1 ratio of DA-9805 (45mg/day), DA-9805 (90mg/day) and Placebo Treatment groups.

Subjects who have provided written informed consent and have met all the inclusion criteria and none of the exclusion criteria will be randomized to one of the treatment groups mentioned in [Table 2-1](#) based on a randomization schedule. An individual, independent of the clinical trial team, will develop the randomization schedules.

The actual randomization assignment will be made through an Interactive Web Based System (IWRS) called WebView (Amarex Clinical Research, Germantown MD). WebView is a Secure Socket Layer (SSL) web portal that allows 24/7 access to clinical trial information. Authorization is based on approved access control list (ACL) that determines a user's access to the site. The Amarex Technology department, who is not otherwise involved with the study, is responsible for the implementation and maintenance of WebView. Each user will be trained in how to use the website. A WebView user manual will be supplied to all study personnel with instructions on using the website.

The Randomization/Supply module of WebView allows authorized users to request randomization (Site Personnel only) into the trial. The detailed description and instructions are included in the

WebView user manual. Amarex Clinical Research has further documentation and validation of WebView specifically with regards to preserving the blinding of this study.

2.4 Blinding

As this is a double-blind trial, the subjects, investigators and their staff, and all Sponsor/CRO personnel involved in the management, and data collection in this study will be blinded to the treatment assignments.

Treatment unblinding for the study will only occur:

1. at the time of final analysis after all clinical data have been received, data inconsistencies/queries have been resolved, and the database is locked
2. for emergency unblinding in the event of safety concerns for individual subjects; these special cases will be documented and reported.

The process for unblinding will be outlined in the Randomization Plan. In addition, any subject with emergency unblinding for any reason will be identified and discussed in the final clinical study report.

3. STUDY ASSESSMENTS/ OUTCOME

3.1 Efficacy Assessments

3.1.1 Primary Efficacy Outcome Measure

The primary efficacy outcome measure for this study is Change in motor MDS-Unified Parkinson Disease Rating Scale (MDS-UPDRS) total score from baseline at week 12.

3.1.2 Secondary Efficacy Outcome Measures:

There are multiple secondary outcomes in this trial as follows:

- Change in total MDS- UPDRS total score from baseline at week 12.
- Change in MDS-UPDRS subscale scores from baseline at week 12.
- Change in Schwab and England (S&E) Scale total score from baseline at week 12.
- Change in Parkinson's Disease Questionnaire (PDQ-39) total score from baseline at week

12.

- Change in Hoehn and Yahr (H&Y) scale total score from baseline at week 12.
- Change in Clinical Global Impression-Severity (CGI-S) and Clinical Global Impression-Improvement (CGI-I) scale score from baseline at week 12.

3.2 Safety Assessments

- Incidence of Treatment-Emergent Adverse Events (AEs).
- Incidence of withdrawals due to AEs.
- Change/shifts in laboratory values.
- Change in vital signs.
- Change in Electrocardiogram (ECG) parameters.
- Change in Columbia- Suicide Severity Rating Scale from baseline at week 12.

4. SAMPLE SIZE DETERMINATION AND RATIONALE

It is planned to randomize a total of 60 subjects (20 subjects per group) with early Parkinson's disease in this trial. This sample size is selected on the basis of clinical judgment and not based on statistical power calculation; it is deemed adequate to provide clinically meaningful descriptive results consistent with the study objectives.

5. INTERIM ANALYSIS

There is no interim analysis planned for this study.

6. ANALYSIS POPULATIONS

6.1 Intent-to-Treat (ITT) population

The Intent-to-Treat (ITT) population is defined as all randomized subjects who have received at least one dose of study treatment and undergone at least one post-randomization efficacy assessment.

6.2 Per Protocol (PP) Population

The Per Protocol (PP) population is defined as the set of subjects who meet the ITT population

requirements, and were not associated with a major protocol violation. This population will be identified before the database lock, and before the treatment assignments are revealed.

The primary analysis of the primary and secondary outcomes will be conducted using the PP population.

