### 5.2 SUBJECT PREMATURE WITHDRAWAL FROM THE STUDY

A subject who is randomized into the study, but who does not complete the study will be considered prematurely discontinued.

All subjects have the right to withdraw at any point during the study without prejudice. It will be documented whether or not each subject completed the clinical study. If for any subject, study treatment or observations were discontinued, the reason(s) will be recorded and the Sponsor should be notified promptly. All efforts must be made to collect data and report records and tests as completely as possible. Reasons for subject withdrawal/discontinuation may constitute one of the following:

- Subject withdrew consent
- Subject chooses to withdraw
- Subject is withdrawn due to an AE
- Pregnancy
- Lost to follow-up
- Subject is treated with or takes a prohibited medication
- The Investigator determines that it is in the subject's best interest
- Excessive protocol deviations, as determined by the Investigator or the Sponsor
- Discontinuation of study by the Sponsor

For subjects who withdraw/are discontinued prematurely, TV3 assessments will be performed as the end of study evaluations. For all withdrawn/discontinued subjects the Follow-up visit will happen 4 weeks  $\pm 3$  days after the end of study Visit evaluations.

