### 7.1 PROHIBITED MEDICATION

The following treatments and medications are prohibited throughout the study

1. Initiation of any anti-parkinsonian medication (including levodopa, dopamine agonists, entacapone and monoamine oxidase-B inhibitors) for the duration of the trial.
2. Initiation of Amantadine or anticholinergics for newly diagnosed subjects or change in the dosage of Amantadine or anticholinergics during the trial for subjects who were on stable doses for 4 weeks prior to screening.

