### **9.11 EFFICACY OUTCOME ANALYSES**

The primary analysis of the primary and secondary endpoints will be conducted using the PP population.

For the efficacy endpoints the data will be summarized and compared according to the variable type. Continuous data summaries will include:

- Descriptive summary of number of observations, mean, standard deviation, median, and minimum and maximum values.
- Inferential statistics include:
  - t-test or ANCOVA using the baseline value as a covariate , if the Normality assumption is met
  - rank –ANCOVA analysis i.e., an ANCOVA analysis on rank-transformed data or other non-parametric methods, if the Normality assumption is not met.

Categorical data summaries will include:

- Frequency counts and percentages.
- Logit model for inferential statistics.
- If the Normality assumption is met, t-test or ANCOVA using the baseline value as a covariate will be used.
- If the Normality assumption is not met, a rank –ANCOVA analysis i.e., an ANCOVA analysis on rank-transformed data or other non-parametric methods will be used.

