7.3 Handling of Missing Data

7.3.1 Handling of Missing Data for Efficacy Evaluations

There is no imputation of missing data planned for efficacy evaluations.

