8.2 Analysis of Efficacy Outcome

The primary analysis of the primary and secondary outcomes will be conducted using the PP population.

To assess the consistency of the Primary Analysis results, a supportive analysis will be conducted using the ITT population. Statistical methodology for the supportive analyses will be the same as that of the primary analysis, with the exception of the analysis population.

All statistical tests for efficacy will be two-sided tests, with $\alpha=0.05$.

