8.2.1 Primary Efficacy Outcome

The primary efficacy outcome for this study is change in motor MDS-Unified Parkinson Disease Rating Scale (MDS-UPDRS) total score from baseline at week 12.

Change in motor MDS-UPDRS total score from baseline at week 12 will be calculated for each subject using the formula in [Section 7.9.5](#). Both Treatment Group 1 and 2 will be compared with Group 3 using Analysis of Covariance (ANCOVA) with baseline value as a covariate to compare the change in motor MDS-UPDRS total score from baseline at week 12. 95% confidence interval

around the difference and P value for the treatment effect will be reported.

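### The primary efficacy comparison uses the per-protocol set and Week 12 scores only, so exits linked to motor outcome can distort it, and the supportive ITT analysis repairs this only in part

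*SAP*

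**What the plan says.** Both documents make the per-protocol (PP) set primary for efficacy. SAP 6.2 has "The primary analysis of the primary and secondary outcomes will be conducted using the PP population", SAP 8.2 repeats it, and protocol 9.11 has "The primary analysis of the primary and secondary endpoints will be conducted using the PP population"; the protocol synopsis agrees. SAP 8.2.1 compares each dose with placebo by "Analysis of Covariance (ANCOVA) with baseline value as a covariate to compare the change in motor MDS-UPDRS total score" at Week 12. SAP 7.3.1 adds: "There is no imputation of missing data planned for efficacy evaluations". The schedule also collects MDS-UPDRS at Weeks 4 and 8, but no planned inference uses those visits. MMRM appears in the protocol's abbreviation list and in no analysis.

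PP is the ITT set less subjects with a major protocol violation, fixed before unblinding. Neither document defines a major violation. Protocol 7.1 prohibits "Initiation of any anti-parkinsonian medication (including levodopa, dopamine agonists, entacapone and monoamine oxidase-B inhibitors) for the duration of the trial". Protocol 5.2 lists among the withdrawal reasons "Subject is treated with or takes a prohibited medication" and "Subject is withdrawn due to an AE". SAP 8.1.2 includes receipt of an excluded drug among its major-deviation categories.

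An ITT analysis is planned as support: "Statistical methodology for the supportive analyses will be the same as that of the primary analysis, with the exception of the analysis population". Under protocol 5.2, early leavers have the TV3 assessments when they exit. The SAP does not say whether those scores count as Week 12.

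**The concern.** The primary comparison is restricted to subjects selected by what happened to them after randomisation. A subject whose motor signs worsen may start an anti-parkinsonian drug and be removed. A subject who does not tolerate treatment may leave before Week 12 and have no score to analyse. If such exits are linked to motor outcome, the arms that remain are no longer the randomised arms.

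Fixing PP membership blind stops the analyst from choosing. It does not stop treatment or disease from choosing. The trial is meant to inform later studies (protocol 1.5), so what is at stake is the efficacy signal carried into them.

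**Working it through.** **Plan's own figure.** There is nothing to reproduce beyond 3 × 20 = 60. SAP 4 states that the sample size rests on clinical judgment. No SD, effect size or exit rate is given.

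**Routes out of each analysis, from the text**

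| Subject | PP Week 12 ANCOVA | ITT Week 12 ANCOVA |
|---|---|---|
| Starts a prohibited drug, has a Week 12 score | Out (natural reading; major violation is undefined) | In |
| Starts a prohibited drug, leaves early | Out | Out, unless the exit score counts as Week 12 |
| Withdraws for an adverse event | In the PP set, but without a Week 12 score | Same |

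The third row matters because an adverse-event withdrawal is not a protocol violation. It acts only through the missing score.

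**Assumed inputs.** SD of change 8. Correlation of change 0.7 between adjacent visits and 0.6 between Weeks 4 and 12. Baseline SD 10, with correlation -0.2 with change. Placebo worsening of 0.5, 1.0 and 1.5 points. Drug effect one-third, two-thirds and full at Weeks 4, 8 and 12. Benefit is placebo change minus active change.

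**Precision.** SE = 8 × √(2/20) = 2.53 points; the 95% CI half-width is about 5.1 points.

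**One arm loses a fraction q.** Suppose removal follows a normal score that correlates r with Week 8 change. The Week 12 mean of those kept, adjusted for baseline, then shifts by approximately

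SD × r × [φ(z)/(1 - q)] × (0.7 - 0.2²), where z is the upper-q normal point.

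For q = 0.20, φ(z)/(1 - q) = 0.280/0.80 = 0.350, and 0.7 - 0.04 = 0.66. This gives:

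- r = 0: 0
- r = 0.3: 8 × 0.3 × 0.350 × 0.66 = 0.55
- r = 0.5: 8 × 0.5 × 0.350 × 0.66 = 0.92
- r = 1: 8 × 1 × 0.350 × 0.66 = 1.85

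Simulation with 1,000,000 subjects per arm agrees. Null rejection rates come from simulated trials of 20 per arm.

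| Removal | True 3.0 becomes | Type I error |
|---|---|---|
| None | 3.0 | about 5% |
| 20% of one arm, at random | 3.0 | about 5% |
| Common rule: more than 8 points worse at Week 8 (19% placebo, 13% active at true 3.0) | 2.5 | 5.1% |
| 20% of one arm, r = 0.3 | 2.4 (placebo) or 3.6 (active) | 5.4% to 5.8% |
| 20% of one arm, r = 0.5 | 2.1 or 3.9 | not tabulated |
| Worst 20% of one arm (r = 1, extreme) | 1.1 or 4.9 | 11% |

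Under the common rule a true 0 stays at 0.0, a true 5.0 becomes 4.2, and the chance of p < 0.05 at true 3.0 falls from 21% to 16%. With SD 6 to 10, the extreme case shifts the estimate by 1.4 to 2.3 points.

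**Which change repairs which route.** Under the common rule, a repeated-measures model on ITT, with Week 12 missing for removed subjects, returns 3.0 and 5.0. The same model on PP returns 2.5 and 4.2, so that route needs the change of set. Adverse-event leavers are already in PP. What helps them is using their Week 4 and 8 scores.

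**Limit of the remedy.** If removal depends on the unseen Week 12 score (more than 8 points worse), repeated measures gives 2.3 for a true 3.0, against 1.9 for ANCOVA on the subjects kept.

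**Exit scores.** Counting a Week 8 exit score as Week 12 gives 3.0 under the common rule. When the worst 20% leave one arm it gives 3.6 (placebo) or 2.2 (active). The unstated rule changes the answer.

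**The case against.** The strongest reply is that this is a phase IIa trial with safety as its primary objective, a sample size described as descriptive, and safety analysed on all dosed subjects. An ITT analysis is already planned, PP is fixed blind, sites must try to make up missed visits (protocol 4.4), and early leavers are assessed at exit. The worsening route is conservative, since it costs 0.5 points, or 0.2 SE, and creates no false positives. Repeated measures relies on missing-at-random and is slightly less precise under the common rule (root mean squared error 2.7 against 2.6); it gains only when removal differs by arm (2.6 against 3.2 when the worst 4 of 20 leave one arm).

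Most of this stands, and it limits the severity. It does not remove the point. The SAP still plans two-sided tests at 0.05 with a confidence interval and P value, and the ITT analysis inherits the Week 12-only method. Exit assessments help only once the SAP says how they are used.

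Three stronger readings are tempting and are not supported:

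- A reader might infer that type I error rises whenever exits differ by arm. Random removal of 20% from one arm leaves it at about 5%. No document links adverse events or non-compliance to motor score.
- A reader might infer that intolerance removes subjects from PP. Adverse-event withdrawal is not a violation. Protocol 6.9 makes withdrawal for continued non-compliance discretionary and does not call it major.
- A reader might take the sentence in protocol 8.11 about subjects who have started PD medication as a plan to rate motor signs after a new drug. It belongs to Part IV (motor complications), not to the Part III motor examination.

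**Conclusion.** The concern holds in a limited form. PP as the primary set and a Week 12-only complete-case ANCOVA leave the comparison open to selection after randomisation, and the ITT analysis closes that gap only for subjects with a Week 12 score. That starting a prohibited drug leads to PP exclusion is the natural reading of the text but remains an inference.

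Under the assumptions above, a common worsening rule biases only a real effect, toward zero. Bias under the null and type I inflation require exits that both differ by arm and track motor outcome. At 20% from one arm the shift is about 0.6 to 0.9 points for moderate correlation. The 1.9 points (0.7 SE) and 11% are an extreme, not an expectation. Neither size nor direction can be known in advance, so the documents do not support a claim that the plan favours the drug. This should be fixed, at moderate severity.

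**What to change.** 1. Make ITT the primary efficacy set and PP supportive, in the SAP (6.2, 8.2) and the protocol (synopsis, 9.11).
2. Analyse change at Weeks 4, 8 and 12 in one repeated-measures model with all three arms: treatment, visit, treatment-by-visit, baseline, baseline-by-visit, unstructured covariance and Kenward-Roger degrees of freedom. Report the Week 12 contrast of each dose with placebo and its 95% CI. Keep the Week 12 ANCOVA as a sensitivity analysis.
3. Assign exit scores to visits by actual study day, for example by midpoints between visits: (28 + 56)/2 = 42 and (56 + 84)/2 = 70, so up to Day 42 is Week 4, Days 43 to 70 are Week 8, and Day 71 on is Week 12. State which score is used when a scheduled and an exit score share a window.
4. Before unblinding, list the deviations that remove a subject from PP, and state how scores after prohibited medication enter the primary analysis. Used as observed, they estimate the effect including the added drug. Set to missing, they estimate the effect without it and rely on missing-at-random. Report the other choice as a sensitivity analysis.

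Delta-adjusted multiple imputation is an optional addition. Protocol 6.1 counts every randomised subject as ITT, while protocol 9.8.1 and SAP 6.1 require a dose and a post-randomisation assessment; aligning them is a reporting matter.

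The cost is text in two documents, with no new data. The downsides are reliance on missing-at-random where Week 12 is missing, inclusion of non-adherent subjects, a few more model parameters, and no gain in precision under a common exit rule.

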6.3 Safety Population

The Safety population is defined as all subjects receiving at least one dose of the treatment after randomization. This population will be used for the analyses of safety parameters.

7. DATA CONVENTION AND RELATED DEFINITIONS

7.1 Baseline Definition

For all parameters, baseline will be defined as the last available value before the randomized treatment.

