## 4.1 SCREENING AND RANDOMIZATION

### 4.1.1 SCREENING VISIT (DAY -14 TO DAY -1), UP TO 14 DAYS

The subject will sign and date the ICF, and Health Insurance Portability and Accountability Act (HIPAA) authorization (according to site practices) prior to any study-related procedures. A subject number will be assigned to each subject in successive order of consent signing at each center, beginning with 001 at each site. Each study site will receive a unique numeric designation, and will precede the subject number (e.g. at study center 01 the first two consented subjects would be 01-001 and 01-002; at study center 02 the first two consented subjects would be 02-001 and 02-002).

Screening Visit procedures are per below:

- Informed Consent will be obtained prior to any study-related procedures. (Refer to [Section 8.1](#))
- Eligibility assessment per the inclusion and exclusion criteria and diagnosis confirmation (Refer to [Section 3.1.2](#) and [Section 3.1.3](#)).
- Subject demographics (Refer to [Section 8.3](#))
- Medical history (Refer to [Section 8.4](#))
- Vital signs (Refer to [Section 8.5](#))
- Height, Weight and BMI (Refer to [Section 8.6](#))
- Physical examination (Refer to [Section 8.7](#))
- List concomitant medications (Refer to [Section 7](#))
- Laboratory assessments (hematology, biochemistry and urine analysis) (Refer to [Section 8.8](#))
- Electrocardiogram (Refer to [Section 8.9](#))
- Urine pregnancy test (Refer to [Section 8.10](#))
- Hoehn and Yahr (H&Y) Scale (Refer to [Section 8.12](#))
- Columbia-Suicide Severity Rating Scale (C-SSRS) (Refer to [Section 8.16](#))
- Clinical Global Impression-Severity (CGI-S) scale (Refer to [Section 8.14](#))
- Mini-Mental State Examination (MMSE) (Refer to [Section 8.17](#))
- Schedule randomization visit

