### 4.1.2 TREATMENT VISIT 0 (TV0): RANDOMIZATION/BASELINE VISIT (DAY 0)

If continued to be eligible for the study at TV0, the subject will proceed to be randomized. All entrance criteria must be met prior to randomization of a subject into the protocol. The following assessments will be performed:

Treatment Visit 0 (TV0) – Prior to Randomization: Perform the following baseline assessments

- Assessment of continued eligibility (Refer to [Section 3.1.2](#) and [Section 3.1.3](#))
- Medical history (Refer to [Section 8.4](#))
- Vital signs (Refer to [Section 8.5](#))
- Body Weight (Refer to [Section 8.6](#))
- Physical Examination (Refer to [Section 8.7](#))
- Electrocardiogram (Refer to [Section 8.9](#))
- Urine pregnancy test (Refer to [Section 8.10](#))

- MDS-UPDRS Scale (Refer to [Section 8.11](#))
- Hoehn and Yahr (H&Y) Scale (Refer to [Section 8.12](#))
- Schwab and England (S&E) Scale (Refer to [Section 8.15](#))
- Parkinson's Disease Questionnaire (PDQ-39) total score (Refer to [Section 8.13](#))
- Clinical Global Impression-Severity (CGI-S) scale (Refer to [Section 8.14](#))
- List concomitant medications (Refer to [Section 7](#))
- Columbia-Suicide Severity Rating Scale (C-SSRS) (Refer to [Section 8.16](#))
- Mini-Mental State Examination (MMSE) (Refer to [Section 8.17](#))
- Randomization (Refer to [Section 9.4](#))

Treatment Visit 0 (TV0) – Post Randomization: Perform the following assessments

- Vital signs (Refer to [Section 8.5](#))
- Study treatment dispensation (Refer to [Section 6.7](#))
- Study treatment first dose administration (Refer to [Section 6.7](#))
- Adverse events evaluation after first dose (Refer to [Section 10](#))

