### 8.16 COLUMBIA-SUICIDE SEVERITY RATING SCALE (C-SSRS)

The Columbia Suicide Severity Rating Scale (C-SSRS) is a widely used suicidal ideation/suicidal behavior assessment tool (Posner, 2011). The C-SSRS assesses both suicidal ideation and suicidal behavior using questions in eleven (11) categories: five (5) for suicidal ideation, five (5) for suicidal behavior, and one (1) for self-injurious behavior without suicidal intent. There is a binary response (yes/no) for each question. For the purpose of this study, the “Lifetime/Recent” version of the C-SSRS, including questions spanning subjects’ lifetime as well as the one (1) month prior to screening will be used as the baseline evaluation. On the following visits the “Since Last Visit” version of the C-SSRS will be used to assess the treatment-emergent suicidal ideation/behavior under study treatment. Suicidal ideation or behavior is defined as a “yes” answer to any one of the 10 suicidal ideation or behavior questions on the C-SSRS. All ratings will be done by a trained interviewer and ideally by the same individual at each study site. Examples for both versions of the C-SSRS to be used are depicted in the text [Figure 18-1](#) and text [Figure 18-2](#).

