8.3.2 Columbia-Suicide Severity Rating Scale (C-SSRS)

All the data from C-SSRS will be listed and descriptive summaries will be presented for each of the subscales (i.e. Suicidal Ideation and Suicidal Behavior).

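### SAP 7.1's single baseline rule conflicts with the protocol's C-SSRS baseline, and the named week-12 change outcome rests on a form that covers only about the last third of treatment

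*SAP*

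**What the plan says.** SAP 7.1 sets one rule for the whole trial: "For all parameters, baseline will be defined as the last available value before the randomized treatment". The SAP makes no exception for the C-SSRS.

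Protocol 8.16 names a specific baseline for this scale. The Lifetime/Recent form asks about the subject's "lifetime as well as the one (1) month prior to screening will be used as the baseline evaluation". At the visits that follow, the Since Last Visit "version of the C-SSRS will be used to assess the treatment-emergent suicidal ideation/behavior under study treatment". The same section defines an event as a yes to any one of the ten ideation or behaviour questions.

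The scale is given at screening, at TV0 before randomization, and at TV1, TV2 and TV3 (Protocol 4.1.1 to 4.1.3 and Table 4-1; SAP Appendix 1). Neither schedule says which version is used at which visit.

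Protocol 9.2.1 and SAP 3.2 name the same safety outcome: "Change in Columbia- Suicide Severity Rating Scale from baseline at week 12". The analysis section, SAP 8.3.2, reads: "All the data from C-SSRS will be listed and descriptive summaries will be presented for each of the subscales", meaning ideation and behaviour. It says nothing about visits, which recall column serves as baseline, or how several post-baseline forms are combined.

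**The concern.** A C-SSRS answer has meaning only together with its recall period, and that period changes with the form and the visit. A general baseline rule and a change to a single visit suit a laboratory value or a rating of current state. They do not suit a scale whose follow-up form asks what has happened since the previous visit.

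Two things follow. The pre-treatment value picked out by SAP 7.1 may not be the one Protocol 8.16 intends, so earlier ideation could drop out of the comparison. And a change read at week 12 cannot by construction reflect an episode reported and resolved at TV1 or TV2.

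Suicidality is a named safety outcome in a first-in-human trial whose primary objective is safety and tolerability. With 20 subjects per arm, one subject classified differently moves an arm's percentage by 1/20 = 5 points. Protocol 3.1.3 excludes subjects who meet criteria for certain psychiatric disorders at screening. It does not exclude past ideation or a positive C-SSRS, so subjects with a yes before treatment can be enrolled.

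**Working it through.** The plan gives no figure on this point to reproduce. The sample size is expressly not power-based, and no test is planned for the C-SSRS. The check compares recall periods.

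**Step 1: baseline period.** Screening falls between Day -14 and Day -1 (Protocol 4.1.1) and TV0 is Day 0.
- Protocol 8.16 baseline: lifetime, plus the month before screening.
- SAP 7.1 baseline, if TV0 uses the Since Last Visit form: the time since screening, 1 to 14 days.
- SAP 7.1 baseline, if TV0 repeats Lifetime/Recent: earlier ideation is still captured, but SAP 7.1 does not say which column (lifetime or recent) is the value.

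Take a subject with yes at screening, no at TV0 and yes at TV3. Under the first SAP reading the record goes from no to yes. Against the protocol baseline it goes from yes to yes.

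Under that same reading the two periods are also unequal: at most 14 days before dosing against a nominal 28 days at TV3. A constant event rate would then give more yes answers at TV3 in every arm, with no drug effect.

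**Step 2: week-12 period.** TV2 is Day 56 ± 3 and TV3 is Day 84 ± 3 (Protocol 4.1.3). Days covered by the TV3 form = TV3 day − TV2 day. Share of treatment time = (TV3 − TV2) / TV3.

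| Case | TV2 | TV3 | Days covered | Share covered | Share outside |
|---|---|---|---|---|---|
| Nominal | 56 | 84 | 28 | 28/84 = 33.3% | 66.7% |
| Shortest | 59 | 81 | 22 | 22/81 = 27.2% | 72.8% |
| Longest | 53 | 87 | 34 | 34/87 = 39.1% | 60.9% |

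If TV2 is missed, the TV3 form reaches further back. A subject with yes only at TV1 or only at TV2 has no at TV3, and so contributes nothing to a change at week 12.

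**Step 3: illustration with assumed rates.** The documents give no event rate. Assume a 12-week event probability p, a constant hazard, each event reported only in the interval in which it occurs, and 20 subjects per arm. The probability of an event in the week-12 interval is q = 1 − (1 − p)^(28/84). The chance that an arm shows at least one event is 1 − (1 − p)^20 over all 12 weeks and 1 − (1 − q)^20 from the week-12 form alone.

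| Assumed p | q | At least one event, TV1 to TV3 | At least one event, week-12 form only |
|---|---|---|---|
| 2% | 0.67% | 33% | 13% |
| 5% | 1.70% | 64% | 29% |
| 10% | 3.45% | 88% | 50% |
| 15% | 5.27% | 96% | 66% |

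**Step 4: does another part of the SAP settle it?** Laboratory values and vital signs are specified by time point (SAP 8.3.3.1, 8.3.4). ECG and physical examination have shift tables from baseline to post-baseline visits (8.3.5, 8.3.6). SAP 8.3.2 has no such structure and does not use the event definition in Protocol 8.16.

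**The case against.** The strongest reply is that the problematic comparison is not actually planned. SAP 8.3.2 governs the C-SSRS analysis. It covers all the data, is not limited to week 12, and contains no change calculation and no treatment-emergent count. The change formula in SAP 7.9.5 is written for effectiveness measurements. Clinically significant findings at any visit are also to be reported as adverse events (Protocol 10.1) and would enter the TEAE tables (SAP 8.3.1). This stands. The documents show an outcome and a baseline rule that do not fit the instrument, alongside an under-specified summary; they do not show a wrong table.

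The second reply is that the TV0 form is unnamed. Protocol 4.1.2 titles TV0 the baseline visit, and Protocol 8.16 describes the Since Last Visit form as assessing events under treatment, which a pre-dose TV0 is not. Against this, 8.16 anchors the recall to screening and assigns the other form to the visits that follow. The baseline part is therefore conditional on the form. The week-12 part does not depend on it.

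The third reply is that ideation absent just before dosing and present on treatment can fairly be called emergent. SAP 7.1 is then the more sensitive rule, and counting only what is new or worse than a lifetime baseline would hide recurrence. This is a sound point, and the fix allows for it. It is also true that the same periods apply to all three arms, so no bias between arms is shown.

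A reader might infer that anyone with ideation before screening and none before dosing would be counted as treatment-emergent. The documents do not support that: the subject would also need a yes on treatment, and the SAP defines no treatment-emergent C-SSRS category.

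**Conclusion.** The point holds as a mismatch to be repaired before unblinding. SAP 7.1 and Protocol 8.16 give different C-SSRS baselines. The named outcome draws on a form that nominally covers 28 of 84 treatment days (33%), or 22 to 34 days (27% to 39%) across the visit windows. That second part rests only on the visit days and the recall period of the form. The first part, a lookback of 1 to 14 days and the possibility that earlier ideation appears as new, assumes that TV0 uses the Since Last Visit form.

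Two stronger readings should be resisted. One is that about two thirds of affected subjects would be missed. The 66.7% is a share of time; turning it into a share of subjects needs onset spread evenly and no persistence or recurrence after TV2, and ideation continuing past TV2 would still show at week 12. The figures in Step 3 rest on similar assumptions and are illustrative only. The other is that early events would be lost. They stay in the listings and may appear in the SAP 8.3.2 summaries or as adverse events; they fall outside the named outcome only.

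**What to change.** 1. In SAP 7.1, exempt the C-SSRS and reconcile its baseline with Protocol 8.16. State which form version is used at each visit, TV0 included, and which recall columns are reported. The behaviour section of the Lifetime/Recent form in Protocol Appendix 5 has a past-3-months column, whereas 8.16 mentions one month, so this should be settled at the same time.
2. In SAP 3.2 and 8.3.2, replace the change at week 12 with the number and percentage of subjects per arm, in the Safety population, with any yes to ideation, and separately to behaviour, at TV1 to TV3. This uses the event definition already in Protocol 8.16 and nominally covers 84 of 84 days. Protocol 9.2.1 carries the same outcome wording, so align it or record the departure in the SAP.
3. Cross-tabulate that result against pre-treatment status, with lifetime, recent and TV0 shown separately. Recurrence in subjects with past ideation is then counted too, not only what is new or worse.

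The cost is SAP wording and one extra table. No new data are needed, and no sample size, alpha or power figure changes.
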